6.1.13.7. Clinical Global Impression-Severity Scale (CGI-S)

The CGI-S scale is a tool used by clinicians to assess the severity of illness in relation to the clinicians previous experience with other patients with that diagnosis ([Guy W. 1976](#)).

6.1.13.8. Quality of Life Enjoyment and Satisfaction Questionnaire Short Form (Q-LES-Q-SF)

The Quality of Life Enjoyment and Satisfaction Scale – Short Form (Q-LES-SF) is a 16-item, self-administered questionnaire that captures an individual's satisfaction with and enjoyment of life. Item scores range from 1 to 5 ([Endicott J. 1993](#)). The Total Score is reported as the percentage of the maximum possible score (Raw Score – Minimum Possible Score / Maximum Possible Score – Minimum Possible Score).

6.1.13.9. Self Report Leibowitz Anxiety Scale (LSAS)

The LSAS questionnaire is a self report rating scale used to assess social anxiety in individuals and has been validated for use as self-report ([Heimberg R. 1999](#), [Baker S. 2002](#)).

6.1.13.10. Toronto Alexithymia Scale (TAS-20)

The TAS-20 is a self-administered assessment looking at how one identifies and describes emotions ([Bagby RM. 2020](#)).

6.1.13.11. Hamilton Anxiety Rating Scale (HAM-A)

The Hamilton Anxiety Scale (HAM-A) is a 14-item, clinician-administered scale that measures severity of anxiety ([Bech P. 1990](#)). Symptoms assessed include those associated with mental agitation, psychological distress, and physical complaints related to anxiety. Items are scored along a range from 0 to 4; the Total Score (sum of all item scores) ranges from 0 to 56. Higher scores reflect greater severity of anxiety symptoms.

6.1.13.12. Montgomery-Asberg Depression Rating Scale (MADRS)

The Montgomery-Asberg Depression Rating Scale (MADRS) is a 10-item, clinician administered interview assessing severity of depressive symptoms ([Fantino B., Moore N. 2009](#)). Item scores range from 0 to 6, with the Overall Score (sum of all item scores) ranging from 0 – 60. Higher scores reflect greater severity of depressive symptoms. This assessment should only be administered to patients with a medical history of depression.

6.1.13.13. CogScreen Symbol Digit Coding test (SDC)

The CogScreen Symbol Digit Coding test (SDC) is a computer-based digit symbol substitution task administered by trained study staff ([Kay G. 1995](#)). SDC measures attention, visual scanning, working memory, and speed of information processing.

6.1.13.14. Conners' Adult ADHD Rating Scale (CAARS)

The Conners' Adult ADHD Rating Scale (CAARS) is a self-report assessment evaluating symptoms and behaviors in adults with ADHD ([Walls B. 2017](#)). This assessment should only be administered to patients with a medical history of ADHD.

6.1.13.15. The PTSD Checklist for DSM-5

The PTSD Checklist for DSM-5 (PCL) is a 20-item self-report measure of the DSM-5 symptoms of PTSD ([Blake D. 1995](#), [Blevins C. 2015](#)). This assessment should only be administered to patients with a history of PTSD.

6.1.13.16. Short Form McGill Pain Questionnaire (SF-MPQ)

The SF-MPQ is a short self-report assessment evaluating pain using sensory and affective subscales from the longer original MPQ assessment ([Melzack R. 1987](#)). This assessment should only be administered to patients with a medical history of chronic pain.

6.1.13.17. Migraine Disability Assessment Questionnaire (MIDAS)

The MIDAS questionnaire is a self-report measure that assesses the impact, level of pain, and disability due to an individual's headaches ([Lipton R. 2001](#)). This assessment should only be administered to patients with a medical history of migraine.

6.1.14. Safety Follow-Up Phone Call

All patients will have a Safety Follow-Up Phone call approximately 7 days after the last study visit (Visit 6 or EOS), unless the patient withdraws from the study prematurely. During this safety follow-up phone call, information on ongoing and new AEs will be collected.

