- Change in Panic Disorder Symptom Severity Scale (PDSS) ([Furukawa TA. 2009](#))-primary efficacy endpoint
- Number of panic attacks
- Change in Clinical Global Impression-Severity Scale (CGI-S) ([Guy W. 1976](#))
- Change in Quality of Life Enjoyment and Satisfaction Questionnaire Short Form (Q-LES-Q-SF) ([Endicott J. 1993](#))
- Change in Leibowitz Social Anxiety Scale (LSAS) ([Heimberg R. 1999](#), [Baker S. 2002](#))
- Change in Assessment of Overall Sleep Quality -- Question #6 from the Pittsburgh Sleep Quality Index ([Buysse DJ. 1989](#))

Exploratory Objective
 
To explore the effectiveness of HB-1 on Common Neuropsychiatric Co-Morbidities.
 
Exploratory Endpoints

 • Change in Toronto Alexithymia Scale (TAS-20) (Bagby R. 2020) • Change in Hamilton Anxiety Rating Scale (HAM-A) (Bech P. 1990) • Change in CogScreen Symbol Digit Coding test (SDC) (Kay G. 1995) • Change in Montgomery-Asberg Depression Rating Scale (MADRS) (Fantino B., Moore N. 2009) only for patients with a medical history of depression • Change in Conners' Adult ADHD Rating Scale (CAARS) (Walls B. 2017) only for patients with a medical history of ADHD • Change in The PTSD Checklist for DSM-5 (Blake D. 1995, Blevins C. 2015) only for patients with a medical history of PTSD • Change in Short Form McGill Pain Questionnaire (SF-MPQ) (Melzack R. 1987) only for patients with a medical history of chronic pain • Change in Migraine Disability Assessment Questionnaire (MIDAS) (Lipton R. 2001) only for patients with a medical history of migraine

Abbreviations: ADHD=Attention deficit hyperactivity disorder; AE=adverse event, DSM-5=Diagnostic and Statistical Manual of Mental Disorders 5th edition; ECG=electrocardiogram, PTSD=post traumatic stress disorder

HB-1 Administration:
 
All patients will receive an oral dose of HB-1 or matching placebo once a day (QD) nightly at bedtime (QHS) with or without food. HB-1 is a proprietary combination of telmisartan and verapamil in a once-daily, extended release formulation.

Study Population:
 
This study will enroll approximately 80 adult patients who meet DSM-5 criteria for the diagnosis of Panic Disorder.

Study Duration:
 
The study will consist of a 12-week treatment period and a one-week post-treatment period for safety follow-up.

Study Centers:
 
Enrollment is anticipated at approximately 8-10 clinical research sites in the United States.

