 - Short Form McGill Pain Questionnaire (SF-MPQ) ([Melzack R. 1987](#)) only for patients with a medical history of chronic pain
 - Migraine Disability Assessment Questionnaire (MIDAS) ([Lipton RB. 2001](#)) only for patients with a medical history of migraine
- Patients will be randomly assigned to either the HB-1 or placebo treatments groups and will be provided with study drug each month while on treatment. Patients will be instructed to take the study drug once a day (QD) nightly at bedtime (QHS) with or without food, at the same time each day with a glass of water.
- Patients who discontinue from the study prior to Week 12: End of study visit (EOS) and all EOS assessments should be performed within 7 days following the discontinuation from the study. Patients who discontinue study treatment prior to Week 12: Patients may discontinue study treatment and remain in the study. Complete the EOS study visit and all EOS assessments within 7 days of study treatment discontinuation. The patient should continue to follow the schedule of assessments through the Safety Follow-Up Phone Call with modified assessments at interim visits including Week 12/Visit 6 as follows:
 - Number of Panic Attacks
 - C-SSRS ([Oquendo MA 2003](#))
 - Efficacy Endpoint Questionnaires
 - Exploratory Endpoint Questionnaires (when applicable)
 - Concomitant Medications
 - Adverse Event Monitoring

¹ Safety Follow-up Phone Call is performed approximately 7 days after Visit 6/EOS.

^m Only the PDSS will be repeated at the Week 2 visit.

ⁿ Placebo-Control Reminder Script (PCRS) ([Cohen, EA. 2021](#)). The PCRS will be administered immediately prior to administering the PDSS at Visits 3-6.

^o CogScreen Symbol1Digit Coding Test (SDC) ([Kay G. 1995](#)); SDC to be done twice at Screening/Visit 1 and no passing score is required.

TABLE OF CONTENTS

INVESTIGATOR PROTOCOL APPROVAL	2
SPONSOR PROTOCOL APPROVAL	3
CONTACT INFORMATION.....	4
PROTOCOL SYNOPSIS	5
LIST OF ABBREVIATIONS AND DEFINITIONS OF TERMS.....	18
1. BACKGROUND	20
1.1. Unmet Need	21
1.2. HB-1 for the Treatment of Panic Disorder	22
1.3. HB-1	23
1.4. Telmisartan	23
1.5. Verapamil Hydrochloride	23
1.6. Study Overview	23
2. OBJECTIVES.....	25
2.1. Primary Objective.....	25
2.2. Exploratory Objective.....	25
3. ENDPOINTS	25
3.1. Safety Endpoints.....	25
3.2. Efficacy Endpoints.....	25
3.3. Exploratory Endpoints	25
4. STUDY DESIGN AND DESCRIPTION.....	26
4.1. Study Design.....	26

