4.4. Monitoring of Adverse Events

Safety will be assessed through the monitoring of Adverse Events (AEs), Treatment Emergent Adverse Events (TEAEs), clinical laboratory assessments, ECGs, Columbia Suicide Severity Rating Scale (C-SSRS) ([Oquendo MA 2003](#)), and orthostatic vital signs. Patients will be monitored for safety from the first dose of HB-1 or placebo at study Week 0 through the Safety Follow-up visit. Serious adverse events (SAEs) will be reported immediately to the sponsor and recorded in the eCRF.

Table 2 below provides guidance on the management of known toxicities that have been associated with verapamil or telmisartan monotherapy. If any of the following criteria are met, the subject will have study treatment discontinued and the Medical Monitor must be informed immediately. Subjects may discontinue study treatment, however, and remain in the study (see [Section 4.5](#)). The stopping criteria listed below will also be captured as adverse events (see [Section 8](#)).

Table 2: Subject Specific Stopping Criteria

Cardiac Disorders	
Hypotension	
 SBP <90 mmHg and DBP <60 mmHg for three consecutive readings 10 minutes apart
Orthostatic Hypotension	
 Decline of ≥ 20 mm Hg in systolic or ≥ 10 mm Hg in diastolic blood pressure after 3 minutes of standing.
New-onset 2 nd or 3 rd degree AV block	
 Grade 1 or higher per CTCAE V5.0*
Sick sinus syndrome	
 Grade 1 or higher per CTCAE V5.0
Atrial flutter	
 Grade 1 or higher per CTCAE V5.0
Atrial fibrillation	
 Grade 1 or higher per CTCAE V5.0
New-onset bradycardia	
 Resting heart rate below 50
New-onset tachycardia	
 Resting heart rate above 120

Onset of angina pectoris	
 Grade 1 or higher per CTCAE V5.0
Congestive heart failure	
 Grade 1 or higher per CTCAE V5.0
Pulmonary edema	
 Grade 1 or higher per CTCAE V5.0
Peripheral edema	
 Grade 2 or higher per CTCAE V5.0
General Disorders	
Urticaria	
 Grade 2 or higher per CTCAE V5.0

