6.1.10. Adverse Events (AEs)

All AEs should be captured on the eCRF from Visit 2/Week 0 through the Safety Follow-up visit. Adverse events considered at least possibly related to study treatment should be followed until resolution, return to baseline, or deemed chronic or stable.

All serious adverse events (SAEs) will be immediately reported to the Sponsor from the time of Visit 2/Week 0 (dosing) through the Safety Follow-up/End of Study Visit.

See [Section 8.2](#) for a full description of the collection and reporting of AEs during this study.

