8.2. Procedures for Recording and Reporting Adverse Events

8.2.1. Recording Adverse Events

Patients will be instructed to report all AEs and will be asked a general health status question at each study visit. All AEs and SAEs occurring in patients will be recorded in the eCRF from Visit 2/Week 0 through the Safety Follow-up Visit after the last dose of drug. An AE will be followed until it is either resolved, has returned to baseline, or is determined to be a stable or chronic condition. All SAEs will be processed as outlined in [Section 8.2.2](#).

At each required visit during the trial, all AEs that have occurred since the previous visit must be reviewed by the Investigator. The Investigator must determine if the AE is serious or non-serious.

The Investigator must assign the following AE attributes:

- AE diagnosis or syndrome(s) if known
 - If not known at time of the report, record the signs and/or symptoms as AEs and provide an updated report with diagnosis when obtained
- Dates of onset and resolution
- Severity as defined per protocol
- Assessment of relatedness to drug
- Action taken with drug as a result of the AE

In general, an AE that is the primary cause of subsequent events should be identified by the primary cause (eg, for dehydration due to diarrhea, the AE would be diarrhea). However, AEs occurring secondary to an initiating event that are separated in time should be recorded as independent events (eg, sepsis secondary to pneumonia, both events should be recorded).

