8.2.2. Reporting of Serious Adverse Events

SAEs will be reported to the sponsor immediately and recorded on the appropriate eCRF and SAE Report Form within 24 hours of the Investigator's first knowledge of the event, even if the experience does not appear to be related to drug, from the Visit 2/Week 0 through the Safety Follow-up visit after the last dose of study drug.

The initial SAE eCRF must be as complete as possible, including details of the current illness and SAE, and an assessment of the relationship between the event and drug. Additional information relating to a previously reported SAE must also be reported within 24 hours of the Investigator's first knowledge of information. The Investigator may also be asked, by the Sponsor or designee, to provide clarifications or additional information.

8.2.2.1. Reporting of Serious Adverse Events to Regulatory Authorities and Institutional Review Board

The Sponsor or designee will determine expectedness of the Sponsor's product for each reported SAE based on the appropriate reference safety information per local requirements. The Sponsor

or designee shall notify regulatory authorities of serious, unexpected, and related AEs or other AEs, per local requirements.

The Sponsor or designee shall notify the Investigator of serious, related, and unexpected AE(s) submitted to the regulatory agencies, per local country requirements.

The Investigator will notify the appropriate IRB of serious, related, and unexpected AE(s), or significant risks to patients, per local country requirements. The Investigator must keep copies of all AE information on file, including correspondence with the Sponsor or IRBs.

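### Protocol 6.1.14 cancels the safety follow-up call for every early study withdrawer, including those who could still be contacted

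*Protocol*

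**What the plan says.** The synopsis (Study Duration) plans 12 weeks of treatment and "a one-week post-treatment period for safety follow-up". The contact that delivers that week is the phone call in Protocol 6.1.14. It is timed about 7 days after the last visit, whether Visit 6 or EOS, and asks about ongoing and new adverse events. It applies to all patients "unless the patient withdraws from the study prematurely".

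Other places describe the call or the AE window without that exception:

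- Table 1, footnote l (repeated in the SAP): "Safety Follow-up Phone Call is performed approximately 7 days after Visit 6/EOS".
- Section 4.4: "Patients will be monitored for safety from the first dose of HB-1 or placebo at study Week 0 through the Safety Follow-up visit".
- Section 6.1.10, AE sentence (repeated in SAP 6.10.2): "All AEs should be captured on the eCRF from Visit 2/Week 0 through the Safety Follow-up visit".
- Section 8.2.1: AEs and SAEs are recorded "from Visit 2/Week 0 through the Safety Follow-up Visit after the last dose of drug".
- Section 8.2.2: SAEs are reported "from the Visit 2/Week 0 through the Safety Follow-up visit after the last dose of study drug".

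On leaving early, section 4.6 allows withdrawal for any reason and asks, where possible, for an EOS visit within 7 days of the last dose. Table 1 footnote k says that the EOS assessments of patients who leave the study before Week 12 "should be performed within 7 days following the discontinuation from the study". Under section 4.5, patients who stop drug but stay in the study keep the schedule, including the call.

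**The concern.** Safety is part of the primary objective, and early leavers are a group in which events around stopping drug matter. For a withdrawer who can still be reached, 6.1.14 removes the only planned contact that would pick up new AEs after EOS. The rule does not turn on whether the patient is willing to be contacted. The protocol is ready to ask a withdrawer to come to the clinic for EOS, yet it rules out the less demanding phone call a week later. What is at stake is the completeness of off-drug AE capture in early leavers. The efficacy analysis is not involved.

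**Working it through.** **The plan's own AE figure.** The sample size section gives about 95% probability of seeing at least one patient with an event of true rate 7.2% in a treatment group. With 80/2 = 40 per arm, 1 − (1 − 0.072)^40 = 0.9497, so it reproduces. The present point does not depend on it.

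**Is withdrawal treated as refusal of contact?** Section 4.6 seeks an EOS visit from patients who withdraw. Withdrawal and refusal of contact are therefore separate in this protocol, and 6.1.14 attaches the exception to the wider of the two.

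**Days off drug at the last planned AE contact.** Inputs:

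- Call 7 days after Visit 6 or EOS (6.1.14, footnote l).
- Window of ±3 days on the call, reading the Table 1 window row as applying to the follow-up column.
- EOS at e = 0 to 7 days after leaving the study (footnote k).
- d = days between the last dose and leaving the study.
- A completer's last dose is taken to be at about Visit 6 (assumption).
- Nominal 7 days is used for the early leaver's call.

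| Patient | Call | Calculation | Days after last dose |
|---|---|---|---|
| Completer | made | 7; window 7 − 3 to 7 + 3 | 7 (4 to 10) |
| Stops drug on leaving (d = 0) | omitted | 0 + 0 to 0 + 7 | 0 to 7 |
| Stops drug on leaving (d = 0) | made | 0 + 7 to 7 + 7 | 7 to 14 |
| Stopped drug d days before leaving | omitted | d + 0 to d + 7 | d to d + 7 |

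**Shortfall against the planned week** = max(0, 7 − d − e).

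- d = 0: from 7 − 0 − 7 = 0 to 7 − 0 − 0 = 7 days.
- General worst case (e = 0): max(0, 7 − d), which is 0 once d is 7 or more.
- Example: drug stopped at Week 4, study left at Week 8, so d = 28 and EOS falls 28 to 35 days after the last dose. No shortfall.

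Section 4.6 counts the EOS window from the last dose and footnote k from leaving the study. At d = 0 they agree, so the 0 to 7 day result does not depend on the choice. The d > 0 rows use footnote k.

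**The case against.** **Leaving the study may mean withdrawing consent.** Section 4.6 requires withdrawal from the study when consent is withdrawn. Protocol 9.1 and SAP 7.7 describe loss from the study in terms of withdrawn consent, and SAP 7.7 expects others to continue. On this reading a further study call might not be permitted. This stands for patients who refuse contact, and the exemption should stay for them. It does not cover everyone, because 4.6 still pursues an EOS visit.

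**A specific rule need not be repeated in general ones.** This is fair. Section 6.1.14 is the section on the call, and the windows elsewhere are general. The SAE sentence of 6.1.10 and the synopsis (Assessment of Safety) join Safety Follow-up and End of Study, and can be read as ending at EOS. So a reader should not infer that every window contradicts 6.1.14. The objection does not answer what the exception does to capture.

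**Other safeguards exist.** Recorded AEs are followed to resolution or stability (8.2.1), patients are told to report AEs, and the TEAE definition has no post-dose cut-off. These cover events already recorded or volunteered. They do not replace a planned contact that asks about new ones.

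**Stronger readings the documents do not support.**

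- A reader might infer that patients removed by the protocol, for suicide risk (6.1.13.6) or unblinded site staff (7.4), lose the call. No clause settles this, but 6.1.14 speaks of the patient as the one who withdraws, and the call is timed from Visit 6 or EOS. Both favour giving them the call. A suicide-risk event is in any case recorded, referred and reported within 24 hours.
- A reader might attribute gaps of 14 or 28 days (the spacing of visits) to the exception. Those arise when no EOS visit takes place, which 4.6 allows for. They are not caused by 6.1.14.
- A reader might infer a loss of AE detection. If 5% to 30% per arm missed the call, and an event of rate 7.2% were visible only after EOS, detection would fall from 0.950 to between 0.942 (n = 38) and 0.877 (n = 28). The documents support neither assumption.

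**Conclusion.** The point holds as a modest, inexpensive improvement. The exception is wider than refusal of contact, and it shortens planned capture of new AEs in reachable withdrawers. Its own effect is a shortfall of 0 to 7 days off drug against the planned week, for patients who stop drug on leaving and attend EOS. It shrinks as the interval between last dose and leaving grows and is nil from 7 days on.

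This rests on EOS taking place as footnote k describes and on a completer's last dose being near Visit 6. The documents give neither the number of patients affected nor any split by arm. Patients who stop drug and stay in the study are not affected. Power, alpha and the efficacy analyses do not change, and no safety conclusion is shown to change. Confidence is medium, because some sites may already read withdrawal as refusal of contact.

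**What to change.** In 6.1.14, limit the exception to patients who withdraw consent to further contact. State there, and in Table 1 footnotes k and l with the SAP copies matched, that all other early study discontinuations get the call about 7 days after EOS. If no EOS visit occurs, make the call about 7 days after the last dose, or as soon as possible after the patient leaves if that is later. This fallback is needed because the call is otherwise timed from a visit that did not happen.

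Optionally, add that patients removed under 6.1.13.6 and 7.4 get the call. This only confirms the more natural reading.

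The cost is one sentence, two footnotes, and at most one extra call per early leaver, of a kind sites already make.

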6.2. Concomitant Medications

6.2.1. Other Concomitant Therapies

Any other medication that is considered necessary for the patient's welfare, including medications for neuropsychiatric disorders (such as SSRI's, benzodiazepines, stimulant medications, antipsychotics, mood stabilizers) and that is not expected to interfere with the evaluation of HB-1 may be given at the discretion of the Investigator. Patients are expected to remain stable on their psychiatric medications throughout the duration of the trial.

Treatment with doses of benzodiazepines that are outside the FDA-approved prescriber's information are excluded.

The following concomitant medications are also excluded per protocol: Inhibitors or inducers of CYP3A4 (erythromycin, ritonavir, telithromycin, rifampin), HMG-CoA Reductase Inhibitors (Simvastatin, Lovastatin, Atorvastatin), Beta Blockers (Timolol eyedrops, Metoprolol), Neuromuscular Blocking Agents (curare-like and depolarizing), Antihypertensive Agents (Prazosin and vasodilators, angiotensin-converting enzyme inhibitors, diuretics, beta blockers, alpha agonists), Inhalation Anesthetics, Disopyramide, Flecainide, Quinidine, Cimetidine, Lithium, Carbamazepine, Phenobarbital, Cyclosporine, Aliskiren, Ramipril and Ramiprilat, aspirin, Theophylline, mTOR inhibitors; sensitive P-glycoprotein substrates (digoxin, fexofenadine, dabigatran etexilate, talinolol, loperamide, vinblastine); grapefruit, grapefruit juice and Seville oranges within two weeks of screening through the last dose of study treatment.

Additionally, patients are required to limit consumption of alcohol to three servings per day defined as: 1 serving of beer=12 ounces (5% alcohol content); 1 serving of malt liquor=8 ounces

(7% alcohol content); 1 serving of wine=5 ounces (12% alcohol content); 1 serving of distilled spirits=1.5 ounces (40% alcohol content)

